5.3 Recruitment

Potential subjects will be identified from the more than 800 patients in the Sickle Celldatabase at Montefiore Medical Center and the ~300 at the University of Pittsburgh. Referrals will be solicited from the New York Metropolitan area and Pennsylvania. We anticipate enrolling 35 subjects at Montefiore and 5 in Pittsburg. [name] has initiated a multidisciplinary SCD/wound care clinic at Montefiore, in collaboration with [name], an associate investigator in this study and a wound expert, which sees about 4 patients per week and draws referrals from many of New York Hospitals. Entry into the study will begin when the subject meets all inclusion criteria and signs an informed consent document to confirm their willingness to participate.

Screening: The subjects will be initially evaluated during a routine clinical visit to determine eligibility, obtain informed consent, have a detailed medical history and physical examination, and have clinical labs that include a hemoglobin electrophoresis for genotype confirmation, unless one is available in the chart within the previous 3 months. Potential subjects will have a detailed assessment of all of their wounds. Methemoglobin level will be drawn to exclude congenital methemoglobinemia. As methemoglobin levels vary with the state of oxygenation and the severity of the anemia and hemolysis, patients who have at least two documented metHb levels below the 3.5% threshold will continue the study even if the meth Hb levels rise above 3.5% during the weeks leading to the first application, as long as they remain below 4.5%. A pregnancy test will be performed for women in reproductive age.

The subject that is deemed eligible will then be scheduled for routine wound care, as determined by the WONC and the PI, of two weeks' time, called the "Run In Period". At the end of the two weeks, the ulcer areas will be measured. Patients whose ulcer total surface area decreases by >25% at the end of the run in period will be excluded from the therapeutic portion

PI: [name]

of the trial.

Standard of care for wounds includes the following:

- Cleanse leg with skin cleanser
- Cleanse ulcer with normal saline & gauze removing any debris from woundbed.
- Apply petrolatum-based ointment around the edge of the wound
- Cover ulcer with non-adhering foam pad if the ulcer size is < 2cm²
- Cover ulcer with Calcium Alginate dressing if the ulcer size is > 2cm²
- Apply 2 layer compression wrap to leg (depending on the condition of theulcer)
- Use of topical or systemic antimicrobials

All participants will be requested to complete the Brief Pain Inventory (BPI) prior to initiation of the therapeutic portion of the trial.

Baseline visit: The following tests will be performed:

- 1. Baseline labs, which include CBC, reticulocyte count, CRP, ESR, LDH, hepatic panel, basic metabolic panel, ferritin, Pro-B Natriuretic Peptide (BNP), urinalysis, urine microalbumin, uric acid, urine pregnancy test (female at reproductive age)
- 2. Research labs: Pax gene, and stored 5-10 cc blood samples
- 3. Saliva for DNA analysis
- 4. The surface area of ulcer(s) will be measured and photographed with defined lighting, distance, exposure and camera type
- 5. A pain assessment tool (VAS assessment)
- 6. Brief Pain Inventory (BPI), ASCQ-ME, PROMIS surveys, Beck Depression Inventory

Screening visit and baseline visits can be combined in one appointment.

After at least two weeks of "run in period", where the patient is treated with standard of care therapies only, the total ulcer surface will be measured and, if there isn't a reduction of>25%, the patient will be randomized to receive sodium nitrite cream or placebo.

A biopsy of the ulcer will be obtained in patients that consent during the run inperiod.

Week 1/Visit 3: First application of "study cream". After cleaning the wound, the wound will be measured by light photography and manually by wound nurse, a microbiome sample will be obtained, and the "study cream" will be applied to all the ulcerated surfaces. Vital signs will be obtained before application to establish baseline MAP and post-application at hours 1, 2, 3, 4, 5. If no significant decrease in MAP pressure from baseline is detected (clinically significant hypotension, or symptomatic dizziness, tachycardia, or hypoxia as per the judgment of the PI), the patient will be discharged and instructed to return for a second application two to three days later. Methemoglobin will be obtained one hour ± 30 min after creamapplication.

Week 2-10/ Visits 4-22: The subjects will be seen twice a week for cream application, wound care and monitoring of side effects. The wound will be measured once a week manually by the wound care nurse and measured by photography after 10±2 applications. Blood pressure and vital signs will be measured upon arrival to outpatient unit and 30 minutes±10 minutes after the application of the study cream, unless clinically indicated. If the blood pressure is stable after cream application for all visit 4, 5, 6, post cream application blood pressure monitoring wound not be needed for future study visits. The wound will be cleaned and study cream will be applied.

Routine bloods will be drawn as clinically indicated. A research methemoglobin level will be obtained every other week.

A repeat pregnancy test will be performed at week 4 in women of reproductive age. Pain assessment: a VAS scale will be obtained with each application of the study cream. If there is more than one ulcer, individual VAS scale per ulcer will be obtained.

After the first three subjects have completed the first application of the study drug, if there are no significant side effects, especially significant changes in BP, patients will be offered the option of applying the second weekly dose of the cream at home, by themselves or by a home health nurse. We will dispense the exact amount of cream to be applied eachweek. This will reduce the number of visits to the wound care / hospital location to once a week.

End of study: Subjects will return the week after the last application to have the study cream removed and for end of study procedures. Blood pressure and vital signs will be measured with a pulse oximeter. The surface area of all ulcerated surfaces will be measured and photographed with defined lighting, distance, exposure, and camera. The wound doctor or nurse will remove the "study cream" and obtain a repeat microbiome sample. A VAS scale will be obtained to assess pain. If there is more than one ulcer, individual VAS scales will be obtained per ulcer. ASCQ-ME, PROMIS, BDI, and BPI surveys will be distributed to the patient. Study labs will be obtained (see Appendix 1). Patients who discontinue the study will still receive end of study procedures.

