5.1 Study Design and Methods

5.2 Overview

This will be randomized, placebo controlled, double blinded study

We plan to enroll fifty subjects with homozygous sickle cell disease (HbSS), sickle-thalassemia (Hb S-ß thalassemia), HbSC, HbSD, or HbSO^{Arab}, in order to have 40 subjects complete at least 8 weeks of treatment, after an expected 20% dropout.

Subjects will receive 2% topical sodium nitrite cream twice a week for 10 weeks or placebo with vehicle only.

Subjects will have 0.1 cm of 2% sodium nitrite cream or placebo cream applied per 1 cm² of the total ulcerated area. If a subject has more than one ulcer, all of them will be treated with either "study cream" or placebo. Areas will be rounded to the nearest 1 cm². If a subject has more than one ulcer and the total sum of all of them is above 100 cm², then one of the ulcers can be enrolled

PI: [name]

^{*} If a patient does not qualify because he/she has an infection at the time of enrollment or at run-in, he/she can initiate the protocol two weeks after the infection has been cleared.

in the study, as long as it does not exceed the 100 cm² size. The other wounds will continue standard of care only. The total amount of sodium nitrite administered to each subject will vary depending upon the size of the ulcer but the treated total surface area will not exceed 100 cm² (i.e., subjects will receive a maximum of 10 cm of sodium nitrite cream).

Administration of study cream or placebo will be double blinded. The pharmacist will not be blinded, so he/she will be aware of who is receiving the investigational drug for safety purposes.

Randomization:

Randomization will be stratified by use of hydroxyurea to minimize its potential confounding effect on the study outcomes; we expect that 50% of participants use hydroxyurea. In addition, within each stratum (use or non-use), random treatment assignment will be balanced, i.e., 1:1 allocation, within blocks. This type of stratified block-randomized allocations will be generated by the study statistician applying a computer algorithm. The randomized allocation will occur once a subject is determined to be eligible for participation after the screening visit and the run in phase, but prior to the first cream application.

Un-blinding Procedures:

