The medical monitor may request unblinding to attribute toxicities if a serious adverse event occurs to determine attribution, or if a dose limiting toxicity occurs to determine if placebo or active treatment was used.

A run in period of at least 2 weeks will be conducted, during which patients will receive/optimize wound care at the Center that will enroll the subjects, following standard of care, routinely available therapies. Patients that experience a reduction of their wound size by >25% during this time will be excluded from the trial, as this suggests an effect secondary to improved wound care only. These patients will remain on protocol and their wound will be measured monthly for up to 6 months or until closure, whichever comes first. If a subject develops an acute vaso-occlusive episode and is hospitalized during the run in period, he/she will have the run in period extended in order to allow the subject to be safely discharged from the hospital and return to outpatient care.

Close monitoring of VSS, especially BP, will be done, to assess changes in patients receiving study cream, compared to placebo.

Measurements of all leg ulcers and photographs will be obtained at the following points: At Baseline

After the 2 weeks run in period, to determine eligibility for study cream application
At mid-point: after 10 applications of study cream, to determine the need for drug modification
At end of study: after the last application of the study cream

An accurate assessment of pain will be obtained each time that size measurements are obtained.

Quality of life questionnaire (ASCQ-Me) will be given before initial application and at the end of protocol or when the ulcer(s) is (are) healed, whatever comes first.

We will monitor metHb level as a safety measure, despite the fact that the phase 1 study did not show significant elevations of metHb. **Teratogenicity** is not a consideration, since the phase 1 study demonstrated minimal systemic absorption of nitrite and nitrate, therefore the risk for the gonads and potential offspring is limited to nonexistent.

Among the entry studies to be obtained, a **3-4 mm skin optional biopsy** may be performed at the edge of the ulcerated area. If the patient has multiple ulcers, the surgeon/wound care expert will decide which one is the safest to biopsy. This will be done

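### Where ulcers total more than 100 cm² and only one is enrolled, the >25% run-in exclusion can be decided by ulcers that get no study cream; the run-in length is also stated inconsistently

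*Combined protocol and SAP*

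**What the plan says.** All references are to the combined protocol and SAP.

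- **Purpose of the rule.** Section 5.2 says: "Patients that experience a reduction of their wound size by >25% during this time will be excluded from the trial". Its reason is that such a fall points to better wound care alone. It speaks of wound size and does not say which wounds.
- **Quantity judged.** Section 5.3 uses the total: "Patients whose ulcer total surface area decreases by >25% at the end of the run in period will be excluded". The randomisation step in the same section repeats it: "the total ulcer surface will be measured and, if there isn't a reduction of>25"%, the patient is randomised.
- **What is measured.** Section 5.2: "Measurements of all leg ulcers and photographs will be obtained at the following points". The points listed include baseline and the end of run-in.
- **What is treated.** Section 5.2 treats every ulcer. The exception is a summed area above 100 cm²: "then one of the ulcers can be enrolled", provided it is itself no larger than 100 cm², and the remaining wounds stay on standard care.
- **Length of run-in.** The screening text in section 5.3 gives two weeks. Section 5.2 and the randomisation step in section 5.3 give two weeks as a minimum. After hospitalisation for a vaso-occlusive episode, section 5.2 adds that "he/she will have the run in period extended", with no maximum. The schedule table puts baseline at about week -2 and run-in at about week -1, without a window.

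**The concern.** The rule is meant to keep out patients whose wounds respond to standard care alone. It does that only if it looks at the wounds the trial will treat and assess. When one ulcer is enrolled out of a total above 100 cm², the other ulcers are in the sum but not in the treatment. A study ulcer that shrank well over 25% on standard care but stayed open can then be randomised, and a static one can be excluded. Nothing in the text limits the rule to the enrolled ulcer or says when that ulcer is chosen.

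At stake is who enters the trial, and so the placebo response. Section 5.2 counts a response as a fall in ulcer size of more than 25%, and calls the study adequately powered if placebo response is below 48%.

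The length issue is separate and can touch any patient. A fixed 25% cut demands a different healing rate for each run-in length, so two sites could apply the rule differently to the same patient.

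**Working it through.** **The plan's own figure.** The documents attach no number to the run-in rule. The nearest figure is the power in section 5.2: above 80% for 88% versus 48%, with 20 completers per arm and two-sided 0.05. With the normal approximation, pooled p = 0.68:

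- z = (0.40 × √20 − 1.96 × √(2 × 0.68 × 0.32)) / √(0.88 × 0.12 + 0.48 × 0.52) = (1.789 − 1.293) / 0.596 = 0.83, power 79.7%.
- Exact enumeration of the uncorrected chi-square test gives 82.1%.

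The stated figure is reproduced, and the fix does not alter it.

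**Which ulcers count.** Let s be the enrolled area, o the other area and T = s + o > 100 cm². The documents give no areas for such patients, so these are assumed.

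- s = 20, o = 90. Study ulcer shrinks 75% to 5, other static: 1 − 95/110 = 13.6%. Randomised.
- Same patient, study ulcer static, other 90 to 60: 1 − 80/110 = 27.3%. Excluded.

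With the other ulcers static, exclusion needs the study ulcer to shrink by more than 0.25 × T/s:

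- 90 enrolled, 20 not: 0.25 × 110/90 = 30.6%
- 50 and 55: 0.25 × 105/50 = 52.5%
- 40 and 65: 0.25 × 105/40 = 65.6%
- 30 and 75: 0.25 × 105/30 = 87.5%
- 20 and 90: 0.25 × 110/20 = 137.5%, which cannot be reached

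So when the enrolled ulcer is under a quarter of the total, its own shrinkage can never trigger the rule. When T is 100 cm² or less, all ulcers are treated, total area equals treated area, and there is no mismatch.

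**Interval.** Assume steady proportional shrinkage r per week, so the fall after w weeks is 1 − (1 − r)^w. The weekly rate that reaches 25% is 1 − 0.75^(1/w):

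- 2 weeks 13.4%; 3 weeks 9.1%; 4 weeks 6.9%; 6 weeks 4.7%
- At 7% a week: 1 − 0.93² = 13.5% at 2 weeks (randomised); 1 − 0.93⁴ = 25.2% at 4 weeks (excluded)

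**Scale of the consequence.** With 20 completers, one more placebo responder adds 1/20 = 5 points. If placebo response were 55% rather than 48% (an assumption), the same formula gives 64.7% power. Nothing in the documents shows that the run-in rule would move it that far.

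**The case against.** The case for leaving this as a minor clarification is substantial.

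- **It is a corner case.** Only patients above 100 cm² in total are affected by the area mismatch. Section 2.4 reports a phase 1 pretreatment area of 4.65 cm², with half the subjects having more than one ulcer. That figure covers treated ulcers only and any phase 1 size cap is not given, but it suggests such totals are uncommon. This stands.
- **Healed ulcers.** A reader might infer that healed study ulcers would be randomised. The documents do not support that: a closed ulcer leaves nothing to treat, and section 7.2 stops study medication on healing. The realistic case is marked shrinkage without closure.
- **Bias.** A reader might infer a biased treatment comparison. Section 5.2 places randomisation after run-in, so the rule acts equally on both future arms.
- **Length.** A reader might infer that run-in has no stated length. Section 5.3 does say two weeks; the defect is disagreement with the other two statements plus an uncapped extension. A longer run-in also removes more standard-care healers, which fits the rule's purpose. A fixed 14-day window with a re-taken reference would admit the 7%-a-week ulcer, which at that rate is 1 − 0.93^10 = 51.6% smaller by week 10. A fixed window is therefore a trade-off and not a clear correction.
- **Infection.** The footnote says that "he/she can initiate the protocol two weeks after the infection has been cleared". A reader might infer that an infected ulcer supplies the reference area. That rests on silence; the natural reading is a fresh start with a new baseline.
- **Weight.** Section 8.1 makes tolerability and adverse effects the primary endpoint, and section 5.2 sets the sample size by feasibility.

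These points limit the finding. They do not answer the literal wording for patients above 100 cm².

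**Conclusion.** The point holds in a limited form. For patients with more than 100 cm² of ulcer and one ulcer enrolled, total surface is the wrong quantity for a rule meant to screen out response to standard care. It can admit a study ulcer that shrank 75% and exclude one that did not change. This rests on reading total literally: no passage says outright that non-enrolled ulcers count, and none says they do not. The effect is on case mix and placebo response. The number of patients is not given and is probably small, and the examples use assumed areas. The comparison between arms is not biased, and the planned 50 subjects and stated power are unchanged.

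On length, the finding is an inconsistency between the two-week statement and the two minimum-of-two-weeks statements, with an extension that has no cap and no stated reference measurement. Section 12.3 describes vaso-occlusive crises as frequent and often leading to admission, but gives no rate, so the number of extended run-ins is unknown.

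**What to change.** In section 5.2 and in both places in section 5.3, apply the >25% rule to the summed area of the ulcer or ulcers that will receive study cream, and require that they be identified before run-in starts. For patients at or below 100 cm² in total, nothing changes.

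Separately, reconcile the statements of run-in length in sections 5.2 and 5.3 and the schedule table, and state which measurement is the reference when run-in has been extended. Which length to adopt is for the trial team.

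The cost is protocol and case report form wording. All ulcers are already measured at baseline and after run-in, so the area rule needs no new data. A repeat measurement would arise only if the team chose to re-take the reference after an extension.

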4.3 Exclusion Criteria

Subjects meeting any of the following criteria during baseline evaluation will be excluded from entry into the study:

- •Exposure to therapeutic nitric oxide, L-arginine, nitroprusside, or nitroglycerine within the past 1 week.
- Subjects presenting with clinically-diagnosed bacterial infection (e.g., osteomyelitis, pneumonia, sepsis, or meningitis).
- •Subjects who have a pre-existing methemoglobinemia (more than 3.5% on two different occasions).
- •Patients who are currently enrolled in any other investigational drug study (this does not include observational or natural historyprotocols).
- •Use of PDE5 inhibitors, such as sildenafil, 4 days prior to screening.
- •Pregnant women (urine or serum HCG +) or nursing mothers.
- The following list of drugs and agents may cause methemoglobinemia and should be avoided while on this study:

Anesthetics (local): Benzocaine, procaine, prilocaine, Anbesol, Orajel

Antimalarials: chloroquine, primaquine, quinacrine

Aniline dyes

Chlorates

Dapsone

Diarylsulfonylureas

Doxorubicin

Metoclopramide

Nitric and nitrous oxide

Nitrobenzenes (shoe and floor polish and in paint solvents)

Nitroethane (artificial nail remover, propellant, fuel additive)

Nitrofurantoin (furadantin)

Pyridium (phenazopyridine)

Phenacetin

Phenylhydrazine

Rasburicase

Sulfonamides (sulfacetamide, sulfamethoxazole, sulfanilamide, sulfapyridine)

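### Low priority: no pregnancy test is listed at Visit 3, so the pregnancy exclusion is last checked at least 14 days before the first cream

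*Combined protocol and SAP*

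**What the plan says.** **Exclusion.** Section 4.3 lists "Pregnant women (urine or serum HCG +) or nursing mothers" and introduces its list with "Subjects meeting any of the following criteria during baseline evaluation will be excluded from entry into the study".

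**Tests before treatment.** Section 5.3 puts a pregnancy test at screening and a urine test among the baseline labs, and allows the two visits to be combined. The schedule of events marks the urine test at baseline (Visit 1, about week -2) and nowhere else before treatment.

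**Interval to treatment.** Section 5.2 states: "A run in period of at least 2 weeks will be conducted". For a subject hospitalised with a vaso-occlusive episode in that period, "he/she will have the run in period extended in order to allow the subject to be safely discharged from the hospital". Allocation is made when the "subject is determined to be eligible for participation after the screening visit and the run in phase, but prior to the first cream application". The schedule puts randomisation at Visit 3, where the first application is also made.

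**Visit 3.** The procedures in Section 5.3 are wound measurement, a microbiome sample, cream application, vital signs and methemoglobin. No pregnancy test is named. The schedule's pregnancy row is blank at run-in and in the Visit 3-4 column.

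**Tests on treatment.** Section 5.3: "A repeat pregnancy test will be performed at week 4 in women of reproductive age". The schedule marks the week 5 column (Visits 11-12) and the end of study.

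**Reproductive risk.** Section 5.2 says teratogenicity "is not a consideration, since the phase 1 study demonstrated minimal systemic absorption of nitrite and nitrate", and concludes that "the risk for the gonads and potential offspring is limited to nonexistent".

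**The concern.** Pregnancy is an exclusion that can change between baseline and first application. The protocol rechecks other conditions over that interval: ulcer area is measured again after run-in, and methemoglobin must stay below 4.5% in the weeks before the first application. Pregnancy has no listed recheck. A conception too recent for the baseline test, or one during run-in, could pass into randomisation and several weeks of applications before the next listed test.

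What is at stake is whether the protocol's own exclusion is applied when exposure starts. No endpoint, analysis or power statement depends on it.

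**Working it through.** The plan gives no interval between pregnancy test and first cream, so there is no stated figure to reproduce. The check is a reading of the schedule plus simple day counts.

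**1. Column placement.** The schedule came from PDF text, so alignment was tested first. The randomisation entry, v3, falls under Visits 3-4, and the photography entry, v13, falls under Visits 13-14, so the columns are intact. The pregnancy row then has marks at Visit 1, Visits 11-12 and Visit 23 only.

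**2. Baseline test to first cream.** The minimum run-in is 2 × 7 = 14 days. No maximum is stated, and hospitalisation lengthens it.

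**3. On-treatment test days.** With day 0 as first cream, week k covers days 7(k − 1) to 7(k − 1) + 6. The schedule's ±3-day window is applied to both weeks.

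| Source | Nominal days | With ±3 days |
|---|---|---|
| Section 5.3, week 4 | 21-27 | 18-30 |
| Schedule, week 5 | 28-34 | 25-37 |

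The two windows overlap on days 25-30.

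**4. Baseline test to next listed test, at the minimum run-in.**
- Week 4: nominally 14 + 21 = 35 days; earliest within the window, 14 + 18 = 32 days.
- Week 5: nominally 14 + 28 = 42 days; earliest within the window, 14 + 25 = 39 days.

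**5. Applications before that test.** The first application is Visit 3, so Visit n is preceded by n − 3 applications. That gives 6 or 7 for a week 4 test (Visits 9-10) and 8 or 9 for a week 5 test (Visits 11-12).

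**6. Number of women.** Section 5.2 plans 50 subjects and Section 9.1 expects equal numbers of men and women: 50 × 0.5 = 25. Counting all of them as of reproductive age makes this an upper figure.

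**7. Order of magnitude for run-in conceptions.** The documents give no conception rate. Assume 2-10% per woman per year.
- 14-day run-in: 25 × 0.02 × 14/365 = 0.019 to 25 × 0.10 × 14/365 = 0.096 in the whole trial, about half of these on active cream.
- Assumed 28-day run-in: 0.038 to 0.192.

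These are conceptions during run-in, not cases that a Visit 3 test would detect. That test can miss a very recent conception, and it can catch one that was too early for the baseline test. The figures show only that the expected number is far below one.

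**The case against.** **The plan applies the exclusion where it says it will.** Section 4.3 ties the criteria to the baseline evaluation, and a test is listed there. That is a fair reading of Section 4.3 alone. But Section 5.2 places the eligibility decision after the run-in, so the plan itself treats eligibility as open until just before first cream.

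**The risk was considered and judged negligible.** This is the strongest point, and it sets the priority. Section 5.2 relies on phase 1 absorption data, which Section 2.4 describes as showing minimal systemic uptake. It does not remove the gap, because the protocol still excludes pregnant women and still tests during treatment. The phase 1 reassurance also comes from 4 weeks of treatment, with high variability between patients, one treated ulcer per subject and a reported pretreatment area of 4.65 cm². The present trial runs 10 weeks and treats up to 100 cm². A reader might infer that the cream is therefore a fetal hazard. Nothing in the documents shows that.

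**The week 4 and week 5 entries conflict.** A reader might take this as a substantive contradiction. It is clerical: the windows overlap, and four completed weeks after first cream is the start of the week 5 column. It would not merit a comment on its own.

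**Pregnancy precautions may exist elsewhere.** Consent pages are absent from the review copy, so one cannot infer that the trial lacks contraception or pregnancy instructions. Such wording would not, however, put a test at Visit 3.

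**Conclusion.** The point stands as a low-priority, inexpensive safety improvement. The last listed test before treatment is at least 14 days before first cream, with no upper limit. The next is at least about 32 days (week 4) or 39 days (week 5) after the baseline test. These counts assume the minimum run-in, the ±3-day window and a baseline test done at the start of run-in.

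The expected number of women affected is very small. Endpoints, sample size and power do not change. The finding is limited to the listed tests not checking the exclusion when exposure begins; it does not show that the treatment is unsafe in pregnancy or that exposed pregnancies are likely.

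**What to change.** 1. In Section 5.3 (Visit 3) and the schedule of events, require a negative urine pregnancy test at Visit 3 in women of reproductive age, read before randomisation and first cream.
2. In Section 4.3, state that the pregnancy exclusion also applies at that point, so that a woman who tests positive is not randomised.
3. Keep one earlier test at screening or baseline, so that the optional run-in biopsy still follows a test.
4. As housekeeping, give one week for the on-treatment test. Changing week 4 to week 5 in Section 5.3 is simplest and keeps the test at the visit with methemoglobin, monitoring labs and physical examination. Retain this test, because Visit 3 can miss a very recent conception.

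**Cost.** The text already lists two tests before treatment. Where screening and baseline are separate, the second can move to Visit 3 at no extra test. Where they are combined, the cost is one extra urine test per woman of reproductive age, at most about 25 in the trial, at a visit that already includes labs. The result must be read before allocation. The rest is short wording changes and a schedule mark, suitable for the next amendment.
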